10.4. Appendix 4: Dose Modifications for Encorafenib-related Adverse Events

Table 19: Recommended Dose Modifications for Encorafenib-related Adverse Events

Worst Toxicity NCI CTCAE Version 4.03 Grade (unless otherwise specified)	Dose Modification for Encorafenib
Eye disorders - Posterior uveitis (including iritis and iridocyclitis)	
Any visual acuity impairment at screening should be documented and should be considered as baseline.	
Grade 1 or 2	
Treat with specific (e.g. topical) ocular therapy. If uveitis does not respond, interrupt dosing of encorafenib and repeat ophthalmic monitoring including visual acuity assessment within 10 days.
 
If resolved to baseline or \leqGrade 1 resume study treatment at the same dose.
 
If posterior uveitis lasts >6 weeks, permanently discontinue encorafenib.

Grade 2	
Treat with specific (e.g. topical) ocular therapy. If uveitis does not respond, interrupt dosing of encorafenib and repeat ophthalmic monitoring including visual acuity assessment within 10 days.
 
If resolved to \leqGrade 1, resume study treatment at one reduced dose level of encorafenib[a].
 
If posterior uveitis lasts >6 weeks, permanently discontinue encorafenib and ophthalmic monitoring should be repeated.

Grade 3	
Interrupt dosing of encorafenib and repeat ophthalmic monitoring including visual acuity assessment within 10 days.
 
If resolved to \leqGrade 1, resume study treatment at one reduced dose level of encorafenib[a].
 
If posterior uveitis lasts >6 weeks, permanently discontinue encorafenib and ophthalmic monitoring should be repeated.

Grade 4	Permanently discontinue encorafenib and immediately follow-up with ophthalmic monitoring[b]
Liver-related adverse events	
Grade 1 AST or ALT $>ULN$ to $3 \times ULN$	Maintain dose level of encorafenib.
Grade 2 AST or ALT >3 to $5.0 \times ULN$ or $3 \times$ baseline value[c] AND blood total bilirubin $\leq 2.0 \times ULN$	
Maintain dose level of encorafenib.
 
If not resolved in ≤ 14 days, interrupt dose of encorafenib until resolved to Grade ≤ 1 (or Grade ≤ 2 in case of liver metastasis), then resume study treatment at current dose level of encorafenib.
 
If additional occurrence:
 
Interrupt dosing of encorafenib until resolved to Grade ≤ 1 (or Grade ≤ 2 in case of liver metastasis), then resume study treatment at one reduced dose level[a] of encorafenib.

AST or ALT 3.0 to $5.0 \times ULN$ AND blood total bilirubin $>2.0 \times ULN$	
Interrupt dosing of encorafenib until resolved to Grade ≤ 1, then:
 
 • If resolved in ≤ 7 days, resume study treatment at one reduced dose level[a] of encorafenib. • If not resolved in ≤ 7 days, permanently discontinue encorafenib.

Worst Toxicity NCI CTCAE Version 4.03 Grade (unless otherwise specified)	Dose Modification for Encorafenib
Grade 3 AST or ALT >5.0 to $8.0 \times$ ULN AND blood total bilirubin $\leq 2.0 \times$ ULN	
Interrupt dosing of encorafenib until resolved to Grade ≤ 1 (or Grade ≤ 2 in case of liver metastasis), then:
 
 • If resolved in ≤ 14 days, resume study treatment at current dose level of encorafenib. • If not resolved in ≤ 14 days, resume study treatment at one reduced dose level[a] of encorafenib. 
If additional occurrence: Interrupt dosing of encorafenib until resolved to Grade ≤ 1 (or Grade ≤ 2 in case of liver metastasis), then resume treatment at one reduced dose level[a] of encorafenib.

AST or ALT $>8 \times$ ULN AND blood total bilirubin $\leq 2.0 \times$ ULN	Permanently discontinue encorafenib.
AST or ALT $>5.0 \times$ ULN AND blood total bilirubin $>2.0 \times$ ULN	Permanently discontinue encorafenib.
Grade 4 AST or ALT $>20.0 \times$ ULN	Permanently discontinue encorafenib.
Cardiac investigation – Prolongation of QT interval QTcF value	
QTcF >500 ms during treatment and change from pre-treatment value remains ≤ 60 ms	
Participants should have regular ECG monitoring (continuous where appropriate) until an adequately trained physician (such as a cardiologist or internist) has reviewed the data. Electrolyte abnormalities including magnesium should be corrected and cardiac risk factors for QT prolongation (e.g. congestive heart failure, bradyarrhythmias) should be controlled.
 
1st occurrence: Temporarily interrupt dosing of encorafenib until QTcF <500 ms. Then resume treatment at one reduced dose level[a] of encorafenib.
 
2nd occurrence: Temporarily interrupt dosing of encorafenib until QTcF <500 ms. Then resume treatment at one reduced dose level[a] of encorafenib. If a participant restarts encorafenib following resolution of Grade 3 QTcF prolongation event, the participant should be evaluated with triplicate predose ECGs on Day 1 of the next cycle, followed by a single postdose ECG and a single predose ECG on Day 15, as well as single predose ECG and a single postdose ECG on Day 1 of the subsequent cycle (2nd cycle after the Grade 3 QT prolongation event).
 
3rd occurrence: Permanently discontinue encorafenib.

QTcF increase during treatment is both >500 ms and >60 ms change from pre-treatment values	
Participants should have regular ECG monitoring (continuous where appropriate) until an adequately trained physician (such as a cardiologist or internist) has reviewed the data. Electrolyte abnormalities including magnesium should be corrected and cardiac risk factors for QT prolongation (e.g. congestive heart failure, bradyarrhythmias) should be controlled.
 
Permanently discontinue encorafenib.

Worst Toxicity NCI CTCAE Version 4.03 Grade (unless otherwise specified)	Dose Modification for Encorafenib
Rash	
Grade 1	
Maintain dose level of encorafenib.
 
Initiate Initial Rash Treatment regimen if it was not already started and rash should be closely monitored.

Grade 2	
Maintain dose level of encorafenib.
 
Initiate Initial Rash Treatment regimen if it was not already started and rash should be closely monitored.
 
Reassess within ≤ 14 days. If rash worsens or does not improve, interrupt dosing of encorafenib until resolved to Grade ≤ 1. Then resume study treatment at current dose level of encorafenib. For dermatitis acneiform, treatment with encorafenib may be maintained if, in the judgment of the investigator, the rash is considered to be unrelated to encorafenib. If treatment with encorafenib was maintained and no improvement within 8 days, interrupt dosing of encorafenib.

Grade 3	
1st occurrence:
 
Interrupt dosing of encorafenib until resolved to Grade ≤ 1. Reassess weekly. Then resume treatment at current dose level of encorafenib.
 
Consider referral to dermatologist and manage rash per dermatologist's recommendation.
 
2nd occurrence:
 
Interrupt dosing of encorafenib until resolved to Grade ≤ 1. Then resume study treatment at one reduced dose level[a] of encorafenib unless in the judgment of the investigator, the rash is considered to be unrelated to encorafenib then study treatment can be resumed at the same dose level.
 
Consider referral to dermatologist and manage rash per dermatologist's recommendation.

Grade 4	Permanently discontinue encorafenib[e].
HFSR/PPE syndrome[d]	
Grade 1	
Maintain dose of encorafenib. Promptly institute supportive measures, such as topical therapy, for symptomatic relief. Give instruction on lifestyle modifications.

Grade 2	
1st occurrence:
 
Maintain dose of encorafenib and HFSR should be closely monitored. Promptly institute supportive measures, such as topical therapy, for symptomatic relief. Give instruction on lifestyle modifications.
 
If no improvement ≤ 14 days, interrupt dosing of encorafenib until resolved to Grade ≤ 1. Resume treatment with encorafenib at current dose level. Continue supportive measures, such as topical therapy, for symptomatic relief. Give instruction on lifestyle modifications.
 
Additional occurrence:
 
Treatment with encorafenib may be maintained or interrupted based upon the investigator's discretion. Continue supportive measures, such as topical therapy, for symptomatic relief. Give instruction on lifestyle modifications.
 
If dosing is interrupted, interrupt until resolved to Grade ≤ 1. Resume study treatment at the same dose level or one reduced dose level[a] of encorafenib at the investigator's discretion.

Worst Toxicity NCI CTCAE Version 4.03 Grade (unless otherwise specified)	Dose Modification for Encorafenib
Grade 3	
1st to 3rd occurrence: Interrupt dosing of encorafenib until resolved to Grade ≤ 1. Promptly initiate supportive measures, such as topical therapy, for symptomatic relief. Give instruction on lifestyle modifications. Reassess the participant weekly. Then resume treatment at one reduced dose level[a] of encorafenib. Consider referral to dermatologist and manage HFSR per dermatologist's recommendation.
 
>3rd occurrence: Interrupt dosing of encorafenib until resolved to Grade ≤ 1, decision to resume treatment with encorafenib at one reduced dose level[a] or permanently discontinue encorafenib should be based upon the investigator's discretion.

SCC, KA and any Other Suspicious Skin Lesion	
Grade ≤ 3	Maintain dose of encorafenib. Treatment of SCC, KA and any other suspicious skin lesion (e.g. new primary melanoma) should occur based upon study site standards.
Diarrhea. Treatment should be based on study site practice	
Uncomplicated Grade 1 or 2	Maintain dose of encorafenib.
Complicated Grade 1 or 2	Consider temporary interruption of encorafenib until resolved to Grade ≤ 1 . Then resume treatment at current dose level.
Grade 3 or 4	Interrupt dosing of encorafenib until resolved to Grade ≤ 1 . Then resume treatment at current dose level of encorafenib if, in the judgment of the investigator, the toxicity is considered to be unrelated to encorafenib, or at one reduced dose level[a].
Nausea/vomiting	
Grade 1 or 2	Maintain dose level of encorafenib. Promptly institute antiemetic measure.
Grade 3	Interrupt dosing of encorafenib until resolved to Grade ≤ 1 . Then resume treatment at one reduced dose level[a] of encorafenib. Note: Interrupt dosing of encorafenib for \geq Grade 3 vomiting or Grade 3 nausea only if the vomiting or nausea cannot be controlled with optimal antiemetics (based on study site standards).
Grade 4	Permanently discontinue encorafenib[e].
All other adverse events (suspected to be related to encorafenib)	
Grade 1 or 2	If the event is a persistent Grade 2 adverse event not responsive to a specific therapy, consider interruption or reduction of encorafenib, as applicable
Grade 3	Interrupt dosing of encorafenib until resolved to Grade ≤ 1 or to pretreatment/baseline level. If the event resolves ≤ 21 days, then encorafenib may be resumed at one reduced dose level[a] based upon the investigator's discretion.
Grade 4	Permanently discontinue encorafenib[e].

Abbreviations: ALT = alanine aminotransferase; AST = aspartate aminotransferase; CK = creatine kinase; HFSR = hand-foot skin reaction; KA = keratoacanthoma; NCI CTCAE = National Cancer Institute Common Terminology Criteria for Adverse Events; PPE = Palmar-plantar erythrodysesthesia; QTcF = QT interval corrected for heart rate using Fridericia's formula; SCC = squamous cell carcinoma; ULN = upper limit of normal.
 
[a] Dose reduction below 150 mg QD is not allowed.
	

Worst Toxicity NCI CTCAE Version 4.03 Grade (unless otherwise specified)	Dose Modification for Encorafenib
	
[b] Ophthalmic monitoring mandated for posterior uveitis: further evaluation with specialized retinal imaging in addition to basic assessment (e.g. best corrected visual acuity testing, slit lamp examination, intraocular pressure and dilated fundoscopy). Any diagnosis of retinal events must be supported by presence or absence of symptoms and visual acuity assessment as well as any other document findings.[c] For participants enrolled with liver metastases and baseline liver function test elevations.[d] Disorder characterized by redness, marked discomfort, swelling and tingling in the palms of the hands or the soles of the feet.[e] A participant with a Grade 4 adverse event may resume encorafenib at the lower dose level if the event recovers to Grade ≤ 1 within 28 days of discontinuing study treatment and, if in the opinion of the investigator and medical monitor, the event is not life-threatening and the participant can be managed and monitored for recurrence of the event. Any participants requiring a dose interruption of duration >28 days must discontinue encorafenib permanently.

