6.6. Dose Modification

Participants will be monitored for adverse events throughout the study. The severity of adverse events will be graded according to National Cancer Institute Common Terminology Criteria for Adverse Events NCI CTCAE Version 4.03 [NCI CTCAE 2010].

If a participant develops toxicity, the dose should be modified as outlined in Appendix 10.4. This table include criteria for interruption, reduction and discontinuation of study treatment. All dose modifications should be based on the worst preceding toxicity. All dosing interruptions and modifications must be recorded in the eCRF.

Individual decisions regarding dose modifications should be made using appropriate clinical judgment, considering relatedness of the adverse event to the study treatment and the participant's underlying condition. Adverse events that have a clear alternative explanation or are transient (≤ 72 hours) abnormal laboratory values without associated clinically significant signs or symptoms may be exempt from dose reduction rules. The investigator should follow the study site supportive guidelines for the management of these toxicities and prophylactic measures.

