6.6.2. Dose Reductions

The dose of encorafenib may be reduced for toxicity management as outlined in **Table 7**. All dose modifications are based on the worst preceding toxicity. Dose reduction below 150 mg QD encorafenib is not allowed.

Table 7: Dose Reductions for Encorafenib

Dose Level	Encorafenib
0 (starting dose)	300 mg QD
-1	225 mg QD
-2	150 mg QD

Abbreviations: QD = once daily
NOTE: Dose reduction should be based on the highest preceding toxicity

If the event causing a dose reduction improves to the baseline level and remains stable for a minimum of 14 days, the dose can be re-escalated to the next dose level at the discretion of the investigator, provided there are no other concomitant toxicities that would prevent re-escalation. There is no limit to the number of times the participant can have their dose reduced or re-escalated (in increments specified in Table 7).

Following any dose reductions occurring due to toxicity, should investigators believe that it is the best interest of their patients, they may re-start and re-escalate doses, with close supervision and monitoring of their patients, except for the following circumstances of dose modification:

- No dose re-escalation of encorafenib is allowed after a dose reduction due to prolonged QTcF \geq 501 msec
- No dose re-escalation is allowed after a dose reduction due to retinal toxicity \geq Grade 2.

7. Discontinuation of Study Treatment and Participant Discontinuation/Withdrawal

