7.1. Discontinuation of Study Treatment for Individual Participants

7.1.1. Temporary Discontinuation and Rechallenge

Adverse events and clinically significant laboratory abnormalities leading to a dose interruption and the conditions for re-starting study treatment (rechallenge) are provided in Appendix 10.4.

A treatment interruption occurs if at least one study treatment administration is missed, followed by a restart of the study treatment.

It may be necessary for a participant to interrupt study treatment to allow for resolution of toxicity (see Section 6.6). Participants may resume treatment if no medical condition or other circumstance exists that, in the opinion of the investigator, would make the participant unsuitable for further participation in the study.

Dose interruptions are also permitted in the case of medical/surgical events or logistical reasons not related to study treatment (e.g. elective surgery, unrelated medical events, vacation, holidays). Participants should be resumed on study treatment within 2 weeks (14 days) of the scheduled interruption, unless otherwise discussed with the Sponsor. The reason for interruption will be documented in the eCRF. Dose interruptions of >4 weeks (28 consecutive days) are not allowed unless approved by the sponsor's medical monitor and study treatment must be permanently discontinued (see **Section 7.1.2**).

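### Table 19 puts Grade 2 posterior uveitis in two rows with different restart doses and nothing to choose between them; Section 7.1.1 also contradicts itself on holds longer than 28 days

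*Protocol*

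**What the plan says.** **Posterior uveitis (Protocol 10.4, Table 19).** The first row is labelled Grade 1 or 2 and the second Grade 2. Both start with ocular therapy, interrupt encorafenib if the eye does not respond, and call for repeat ophthalmic monitoring within 10 days. On resolution, the first row says to "resume study treatment at the same dose" and the second to "resume study treatment at one reduced dose level of encorafenib". From the starting dose, Table 7 makes one reduced level 225 mg.

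**General rules (Protocol 6.6 and 6.6.2).** "All dose modifications should be based on the worst preceding toxicity". Also, "Individual decisions regarding dose modifications should be made using appropriate clinical judgment". If the event returns to baseline and "remains stable for a minimum of 14 days, the dose can be re-escalated to the next dose level", at the investigator's discretion.

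**Elsewhere in Table 19.** For a repeat Grade 2 hand-foot skin reaction the choice is handed over openly: "Resume study treatment at the same dose level or one reduced dose level[a] of encorafenib at the" investigator's discretion. For Grade 2 AST/ALT the table gives one restart dose for the first event and a lower one for an additional occurrence.

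**Long holds (Protocol 7.1.1).** "Dose interruptions of >4 weeks (28 consecutive days) are not allowed unless approved by the" sponsor's "medical monitor and study treatment must be permanently discontinued". Section 6.6.1 and the matching bullet in Section 7.1.2 require discontinuation after more than 28 consecutive missed days; they cross-refer to Sections 7.1 and 7.1.1 respectively. Table 19 footnote [e] requires discontinuation and mentions no exception.

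**The concern.** A site with a Grade 2 event that has resolved finds two applicable instructions with different doses. The rows differ in label and in other wording, so this is not a line duplicated when the PDF was read.

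Uveitis-type events are adverse events of special interest (SAP 5.6.2). Events leading to dose reduction are tabulated separately from those leading to interruption. Both feed the Trial Steering Committee's tolerability judgment (SAP 5.8.1). The event counts as an interruption under either row, but as a reduction only under the second. With three to six evaluable participants, one reclassified event is visible.

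The restart dose also enters the Cycle 1 dose-intensity calculation, and so can decide whether a participant is evaluable or is replaced.

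**Working it through.** **1. Does anything select a row?** The worst preceding grade is 2 under both rows, so that rule cannot choose. The clinical-judgment sentence is general and stands in the section that sends sites to Table 19. The hand-foot and AST/ALT entries show how the table words discretion or an occurrence condition when it means one; the uveitis rows have neither.

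**2. Restart dose.** 300 − 225 = 75 mg per day; 75/300 = 25%.

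**3. DLT status.** Table 4 makes uveitis a DLT at Grade 3 for more than 21 days or at Grade 4. Grade 2 is not a DLT, so the participant must meet the 75% requirement to be evaluable.

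**4. Cycle 1 dose intensity.** The planned dose is 28 × 300 = 8400 mg, as in SAP 5.6.1. The threshold is 0.75 × 8400 = 6300 mg, so the tolerable loss is 2100 mg. Let n be the full-dose days before the hold, g the held days, and r = 28 − n − g the days after restart. The documents give no hold timing, so n and g are assumptions.

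- Same-dose row: the loss is 300g, and 300g ≤ 2100 when g ≤ 7. For g ≥ 8 both rows fail and agree.
- Reduced row, returning to 300 mg 14 days after restart: the loss is 300g + 75 × min(r, 14). For g ≤ 3 it is at most 900 + 1050 = 1950, so both rows pass. For g = 4, 5, 6 and 7 it exceeds 2100 when n ≤ 11, 14, 17 and 20.
- Disagreements: 11 + 14 + 17 + 20 = 62.
- Reduced row with no re-escalation: it passes when n ≥ 3g, so disagreements number 2 + 5 + 8 + 11 + 14 + 17 + 20 = 77.
- If the 14 days run from the first held day, k = 14 − g days are spent at 225 mg; g = 4 then passes (1200 + 750 = 1950), leaving 14 + 17 + 20 = 51.

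Share of patterns with n ≥ 1 and r ≥ 1, re-escalating 14 days after restart:

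| Holds considered | Any start | Hold starts Day 8 or later (n ≥ 7) |
|---|---|---|
| 1–7 days | 62/161 = 38.5% | 38/119 = 31.9% |
| 1–10 days | 62/215 = 28.8% | 38/155 = 24.5% |
| all | 62/351 = 17.7% | 38/210 = 18.1% |

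These are counts of patterns, not probabilities.

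Examples:

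- n = 14, g = 5, r = 9: 6900/8400 = 82.1% against (4200 + 2025)/8400 = 74.1%. The rows disagree.
- n = 14, g = 3, r = 11: 7500/8400 = 89.3% against (4200 + 2475)/8400 = 79.5%. Both are evaluable.

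**5. Cycle 2 Day 1 PK.** Take n = 15, g = 5, r = 8: 6900/8400 = 82.1% against (4500 + 1800)/8400 = 75.0%, evaluable under both rows. Under the reduced row the participant takes 225 mg from Day 21 and, unless re-escalated, still does so on Day 29. SAP 5.7.1.1.3 drops from the summary statistics anyone with a missed or reduced dose in the three days before, or on, Cycle 2 Day 1. SAP 5.6.1 defines a reduction as a fall from the previous non-zero dose, which happens here only on Day 21, outside the window. The same section elsewhere treats any day below the planned dose as reduced. The outcome depends on which meaning applies. If the profile is dropped and only three participants have PK data, 3 − 1 = 2 is below the SAP minimum of three for a mean and CV; individual values are still listed.

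**6. Holds over 28 days.** Section 7.1.1 states an exception and a mandatory stop in one sentence. Sections 6.6.1 and 7.1.2 point back to it or to its parent section, so they may import the exception. Footnote [e] has no such cross-reference.

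**The case against.** The table is headed as recommended modifications, individual decisions call for clinical judgment, and both doses are permitted levels. The dose difference need not last, because Section 6.6.2 allows re-escalation. A non-evaluable participant is replaced. The event has to be Grade 2 posterior uveitis that fails ocular therapy, and no incidence is given. All of this stands and limits the size of the problem. It does not tell a site which row to use.

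Four stronger readings are tempting, and the documents do not support them:

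- *The DLT assessment or sample size is compromised.* Grade 2 uveitis is not a DLT, and the decision rule does not use the restart dose.
- *A restart approved by the medical monitor after more than 28 days breaches Sections 6.6.1 and 7.1.2.* Their cross-references to 7.1 and 7.1.1 may carry the exception with them. The firm inconsistencies are within the 7.1.1 sentence and with footnote [e]. That footnote is attached to Grade 4 entries, although its last sentence covers any participant.
- *Cycle 2 Day 1 PK data would be lost.* This holds only under one of the two meanings of a reduced dose in the SAP.
- *Evaluability changes in over a third of cases.* The 38.5% counts patterns on a grid that stops at 7-day holds. It also includes holds from Day 2, which is early given that ocular therapy must fail first.

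**Conclusion.** The concern holds as a contradictory dosing instruction for an adverse event of special interest. From the starting dose the restart is 300 or 225 mg under rules of equal standing, and the count of events leading to dose reduction changes with the choice. An effect on Cycle 1 evaluability is possible only with holds of up to 7 days (4 to 7 days if re-escalation follows 14 days after restart). Its frequency is unknown, and its cost is one replacement participant. An effect on the PK summaries is conditional on how the SAP wording is read. The primary endpoint definition, the DLT rule and the sample size are untouched.

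The long-hold wording is a secondary drafting fault. It should be corrected because one sentence cannot both allow and forbid continuation. The whole point is modest in consequence and cheap to correct, so it should be corrected.

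**What to change.** **Table 19.** Make the two uveitis rows mutually exclusive. Only the sponsor can say which dose was intended, so there are two options:

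- Label the first row Grade 1, with a restart criterion that works for Grade 1 (for example, resolved to baseline or Grade 0, same dose), and let Grade 2 restart one level lower. Changing the label alone is not enough: the row's present criterion accepts Grade 1, so a Grade 1 event would already meet it when the hold began.
- Keep Grade 2 in both rows, with the same dose for a first occurrence and one level lower for an additional occurrence, as in the Grade 2 AST/ALT entry.

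**Section 7.1.1.** State one rule for holds over 28 consecutive days. Align footnote [e] with it, and check that Sections 6.6.1 and 7.1.2 read the same way.

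**Cost.** A short protocol amendment with IRB/IEC approval (Protocol 10.1.1) and a letter to the two or three sites. Under the first option some Grade 2 participants restart at a lower dose than the present first row would give. No procedures are added.

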4.1.1. Study Design Overview

This is a phase 1, multicenter, open-label, single-arm study to investigate the safety and tolerability of encorafenib monotherapy in adult Chinese participants with *BRAF* V600E mutant advanced solid tumors (unresectable metastatic melanoma or metastatic NSCLC) who are *BRAF*- and *MEK*-inhibitor treatment-naïve and have failed the previous therapy(ies) for advanced metastatic disease or are not eligible to standard therapy. Participants will be eligible for the study based on identification of a *BRAF* V600E mutation in tumor tissue by a local National Medical Products Administration (NMPA) approved assay obtained prior to screening.

All participants will receive a fixed flat oral dose of 300 mg encorafenib QD.

It is planned to enrol up to six evaluable participants using a 3+3 design, shown in Figure 1.

Figure 1: Schema of 3+3 Design

Abbreviations: DLT = dose limiting toxicity; TSC = Trial Steering Committee

- Three participants will initially be enrolled and will be evaluated for DLTs during the first cycle of treatment (28 days) [the DLT evaluation period]:

- If there are no DLTs in the first three participants in the DLT evaluation period, enrollment will be stopped.
- If one of the first three participants experiences a DLT in the DLT evaluation period, a Trial Steering Committee (TSC) will make the recommendation whether three additional participants will be enrolled to expand the number of participants to a total of six.
- If more than one of the first three treated participants experience a DLT, enrollment will be stopped.
- If the group is expanded and two or more of the six participants experience a DLT, enrollment will be stopped.

A DLT is defined as any adverse event or abnormal laboratory value assessed as unrelated to disease, disease progression, intercurrent illness or concomitant medications/therapies that satisfies at least one of the criteria listed in **Table 4**.

Table 4: Criteria for Defining Dose Limiting Toxicities

Toxicity		Any of the following criteria
Blood and lymphatic system disorders[a]		≥Grade 3 neutropenia (ANC <1.0 × 10 ⁹ /L) for >7 consecutive days
		≥Grade 3 thrombocytopenia (platelets <50 × 10 ⁹ /L) for >7 consecutive days
		Grade 4 thrombocytopenia
		Febrile neutropenia (ANC < 1.0 × 10 ⁹ /L with fever ≥38.5°C)
Investigations (renal)		≥Grade 3 serum creatinine
Investigations (hepatic)		≥Grade 3 blood bilirubin (> 3 × ULN)
		≥Grade 3 ALT or AST for > 7 consecutive days

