5.1. Inclusion Criteria

All the following inclusion criteria must be met for a participant to be eligible for this study:

1. Provide a signed and dated informed consent form (ICF).
2. Chinese male or female with age ≥ 18 years old at the time of the informed consent.
3. Documented histology- and/or cytology-confirmed metastatic melanoma or NSCLC (i.e. adenocarcinoma, large cell carcinoma, squamous cell carcinoma).
4. Presence of *BRAF* V600E mutation as determined by a local laboratory with a NMPA approved *BRAF* test.
5. *BRAF* inhibitor treatment-naïve participants and having failed the previous therapy(ies) for metastatic disease or are not eligible to standard therapy.

Note:

Alternative chemotherapy regimen is permitted if participants were platinum intolerant or ineligible.

6. At least one tumor lesion as per investigator assessment according to RECIST Version 1.1, which has neither been irradiated nor biopsied during the screening period. The irradiated lesion is acceptable only if it is proven as disease progression deemed measurable prior to study.
7. Life expectancy ≥ 3 months.
8. ECOG performance status of 0 or 1.
9. Adequate hematologic function at screening and baseline characterized by the following:
 - a. *Absolute neutrophil count $\geq 1.5 \times 10^9/L$.*
 - b. *Hemoglobin ≥ 90 g/L.*
 - c. *Platelets $\geq 100 \times 10^9/L$.*

d. *International normalized ratio, prothrombin time or (activated) partial thromboplastin time $\leq 1.5 \times$ upper limit of normal (ULN).*

10. Adequate hepatic function at screening and baseline characterized by the following:

- Total bilirubin $\leq 1.5 \times$ ULN.*
Note: Total bilirubin $> 1.5 \times$ ULN is allowed if indirect bilirubin is $\leq 1.5 \times$ ULN.
- Alanine aminotransferase and aspartate aminotransferase $\leq 2.5 \times$ ULN or $\leq 5 \times$ ULN in case of documented liver metastases.*

11. Adequate renal function at screening and baseline characterized by the following:

- Serum creatinine $\leq 1.5 \times$ ULN.*
- Creatinine clearance ≥ 50 mL/min as calculated by the Cockcroft-Gault formula; or estimated glomerular filtration rate > 50 mL/min/1.72m².*

12. Able to comply with the study protocol as per investigator assessment including oral drug intake, complying scheduled visits, treatment plan, laboratory tests and other study procedures.

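### Table 19 puts a transaminase value of three times baseline in the maintain row and also in the interrupt or permanent-discontinuation row for participants with liver metastases and raised baseline tests

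*Protocol*

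**What the plan says.** The relevant text is the liver block of Table 19 in Protocol Section 10.4 (Appendix 4), at total bilirubin no higher than 2.0 × ULN.

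- **Grade 2 row.** It opens with "Grade 2 AST or ALT >3 to" 5.0 × ULN and adds, as an alternative, three times the "baseline value[c] AND blood total bilirubin" at or below 2.0 × ULN. The first action is to keep the dose. Dosing is interrupted only if the event has not resolved within 14 days.
- **Footnote [c].** It defines who the alternative is for: "For participants enrolled with liver metastases and baseline liver function test elevations".
- **Grade 3 row.** "Grade 3 AST or ALT >5.0 to" 8.0 × ULN: interrupt dosing.
- **Row above 8 × ULN.** The action is to "permanently discontinue encorafenib".

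Neither of the last two rows has a baseline term in its entry limits or an exception for footnote [c] participants.

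Inclusion criterion 10 (Section 5.1) caps ALT and AST at 2.5 × ULN in general and at 5 × "ULN in case of documented liver metastases".

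The Grade 2 interruption ends at Grade 1 or lower, or at Grade 2 or lower "in case of liver metastasis), then resume study treatment at current dose level of encorafenib".

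A footnote to Table 8 (Section 8.3.4) names Appendix 10.4 as the place for liver stopping criteria and required actions. Sections 6.6 and 6.6.2 say that dose changes follow the worst toxicity so far.

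**The concern.** A dose-modification table works only if each laboratory result leads to one row. Here the Grade 2 row has a limit that moves with the participant's baseline, while the more severe rows at the same bilirubin level are fixed in ULN. For participants who enter with raised transaminases, the moving limit can cross the fixed ones. Two sites could then act differently on the same result while each follows the table.

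The first stake is patient care, because one of the instructions is a permanent stop. The second is the evidence. Under Sections 4.1.1 and 9.7, the Trial Steering Committee judges 300 mg QD partly on adverse events leading to interruption, reduction or discontinuation. With three to six evaluable participants, one such event is 1/6 = 17% to 1/3 = 33% of the sample.

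**Working it through.** **Inputs.** Write the baseline as b × ULN. Footnote [c] requires an elevated baseline and inclusion criterion 10 caps it, so 1 < b ≤ 5. Bilirubin is at most 2.0 × ULN. The fixed limits from Table 19 are 3, 5 and 8 × ULN.

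**Crossing points.** 3b > 5 when b > 5/3 = 1.67. 3b > 8 when b > 8/3 = 2.67. At the entry limit, 3b = 3 × 5 = 15.

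| Baseline (× ULN) | 3 × baseline (× ULN) | Rows met |
|---|---|---|
| 1.5 | 4.5 | maintain only |
| 2 | 6 | maintain and interrupt |
| 2.5 | 7.5 | maintain and interrupt |
| 3 | 9 | maintain and permanent stop |
| 4 | 12 | maintain and permanent stop |
| 5 | 15 | maintain and permanent stop |

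**Does the result depend on the reading?** The alternative carries no comparator sign, so four readings are possible.

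1. *Exactly 3b.* Overlap as in the table.
2. *Upper limit (above 3 × ULN up to 3b).* The overlap is wider. At b = 4 it runs over >5 to 8 × ULN with the interrupt row and over >8 to 12 × ULN with the stop row.
3. *Lower limit without a cap (3b or more).* Overlap occurs for every b > 1. At b = 2 it covers 6 to 8 × ULN with the interrupt row and everything above 8 × ULN with the stop row.
4. *Lower limit capped at 5 × ULN.* No overlap. But the band from 3b to 5 is empty once b > 1.67. For smaller b it lies inside the >3 to 5 × ULN band that the row already covers, because b > 1 gives 3b > 3. The alternative then adds nothing.

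The rows with bilirubin above 2.0 × ULN stay separate, provided that the bilirubin condition governs both limbs of the Grade 2 row. The interrupt and stop rows do not overlap each other.

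**The Grade 2 interruption.** Take a participant with liver metastases whose value stays at 4 × ULN. It lies in the >3 to 5 × ULN band, so it is Grade 2. After 14 days without resolution the row interrupts dosing until Grade 2 or lower. The value is already Grade 2, so the trigger and the resume condition hold together.

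**The case against.** The strongest reply is that the text already points to the more severe row. Table 19 is keyed to the worst toxicity grade, Sections 6.6 and 6.6.2 repeat that principle, and values above 5.0 to 8.0 × ULN are labelled Grade 3. A careful site would probably lean that way. But the principle concerns which toxicity to act on; it does not say how to classify one value that meets two rows. Used as a tie-breaker it also voids the alternative: a value of 3b is either at most 5 × ULN, where the fixed limit already covers it, or above 5 × ULN, where it is overruled.

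It can also be said that the table is titled as recommendations and that Section 6.6 leaves room for clinical judgment. That is true, but judgment is not a precedence rule, and Table 8 refers to this appendix for required actions.

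Three limits stand. The conflict concerns only participants with both liver metastases and raised baseline tests. Reading 4 removes it, at the price of an alternative without effect. And the resume-condition problem is clear only for values of >3 to 5 × ULN; at 6 or 9 × ULN, Grade 2 or lower on the ULN scale is not already met.

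A reader might go further and infer that the DLT table is faulty, because "Grade 3 ALT or AST for > 7 consecutive days" has no baseline term and a drift from 4.9 to 5.1 × ULN would satisfy it. The documents do not support that. Under Section 4.1.1 a DLT must also be assessed as unrelated to disease, and the committee judges whether toxicities are significant. Grading DLTs by CTCAE is a design choice.

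**Conclusion.** The point holds as an internal contradiction in Table 19. On readings 1 and 2, an eligible footnote [c] participant meets the maintain row and the interrupt row once baseline exceeds 1.67 × ULN, and the maintain row and the permanent-stop row once it exceeds 2.67 × ULN. On reading 3 the overlap begins at any raised baseline. On reading 4 the alternative has no effect. The rule is therefore either contradictory or inoperative. The overlap between the Grade 2 trigger and its resume condition is a separate defect.

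The documents give no rate for liver metastases, raised baseline tests or on-study rises, so the number affected is unknown; in a study of this size it is probably small. The width of the baseline range above 2.67 × ULN is not a frequency and should not be read as one.

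A reader might also infer an effect on the DLT count or on evaluability. Neither is shown. The DLT criteria apply whichever Table 19 row a site uses. Falling below 75% of the 8400 mg planned for Cycle 1 (SAP Section 5.6.1) means receiving less than 6300 mg. Seven missed 300 mg doses leave exactly 6300 mg, so at least eight must be missed, and a participant with a DLT stays evaluable anyway. What can change is patient management and the interruption and discontinuation counts that the committee reviews. Because the rule governs permanent stopping for liver toxicity, it should be corrected even if it is rarely used.

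**What to change.** The sponsor should reconcile the liver rows of Table 19 with footnote [c], so that for these participants each combination of ALT/AST and bilirubin falls in exactly one row. The text should say whether the ULN-based or the baseline-based limit governs, give the alternative a comparator sign, and carry the decision through the Grade 2, Grade 3 and above-8 × ULN rows. It should also separate the Grade 2 interruption trigger from its resume condition for participants with liver metastases. Which rule holds is for the sponsor's clinical team to decide.

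A simple check is to run baselines of 1.5, 2, 3 and 5 × ULN through the revised rows and confirm that each value has one instruction.

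The cost is wording in one protocol table and its footnote, with no added procedures or participants. Protocol Table 4 and SAP Table 2 need no change on this account.
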